14.4. AUDIT AND INSPECTION

An audit may be conducted at any time by persons appointed by the sponsor and independent of the persons conducting the research. Its purpose is to verify the participants' safety and respect for their rights, compliance with applicable regulations and the reliability of data.

An inspection can also be carried out by a competent authority (ANSM for France or EMA in the context of a European study, for example).

The audit, as well as the inspection, can be applied at all stages of the research, from the development of the protocol to the publication of the results and the classification of the data used or produced as part of the research.

Investigators agree to comply with the sponsor's requirements as regards an audit and the competent authority for a research inspection.

15. ETHICAL AND REGULATORY CONSIDERATIONS

DATA PROTECTION

Once all data are collected on eCRF, and data extracted from the SNDS database are received by the BPE research platform, data management and statistical analysis will be carried out by the BPE research platform in accordance with the requirements of the French legal and regulatory framework governing, particularly for the access to the data of the SNDS: the order of March 22nd, 2017 on security standard applicable to the national health data system and the order of July 17th, 2017 on the reference terms determining confidentiality, expertise and independence criteria for research laboratories and research firms.

To store individual data extractions from the SNDS, the BPE research platform has added in its IT system an internal secured network (cut off from the outside), called "Bulle BPE" which was initially homologated on November 23rd, 2018, and on March 22nd, 2019. All study data will be hosted in the "Bulle BPE" with a limited and restricted access to authorized persons involved in the study project. Access to users' sessions needs strong 2-level authentication, and all the user's activities in the "Bulle BPE" are registered. The physical access to the office hosting the treatment is controlled by input-output badge, digital code, intrusion alarm connected to a security PC and a video surveillance system. To guarantee data confidentiality, only the full date of care will be kept on the 5 so-called sensitive variables and the other so-called sensitive variables will be truncated (year of birth, month and year of death, department of residence and department of death).

REGULATORY ASPECTS

The sponsor and the investigator(s) undertake to ensure that this research is carried out in accordance with law no. 2012-300 of 5 March 2012 on research involving the human person, as well as in agreement with Good Clinical Practices (ICH version 4 of 9 November 2016 and the decision of 24 November 2006) and the Declaration of Helsinki (which can be found in full at https://www.wma.net).

The research is conducted in accordance with this protocol. Except in emergency situations that require the implementation of specific therapeutic acts, the investigator(s) undertake(s) to respect the protocol in all points especially with regard to the collection of subject informed consent, and notification and follow-up of serious adverse events.

This research has received a favourable opinion from the Committee for the Protection of Persons (CPP) by CPP Sud Est I.

The CHU de Bordeaux, sponsor of this study, has taken out a civil liability insurance contract with HDI GLOBAL SE in accordance with the provisions of the Public Health Code.

The data recorded during this research will be subject to computerised processing, i.e. the BPE research platform, in accordance with:

• EU regulation 2016/679 of the European Parliament and European Council, dated 27th April, 2016, pertaining to the protection of natural persons with regard to the processing of personal data and on the free movement of such data, and repealing Directive 95/46/EC (General Data Protection Regulation); and

• law 78-17, known as "Informatique et Liberté", dated 6th January, 1978 and relating to the processing of data files and freedoms; law 2018-493, dated June 20th, 2018 and relating to the protection of personal data, modifying Law No. 78-17; and Law No. 2004-801, dated 6th August, 2004, on the protection of individuals with regard to the processing of personal data.

The BPE research platform has declared the research to the French National Commission for Informatics and Liberties (CNIL). The SNDS study is a database analysis with individual anonymous information for which subject informed consent is not required. Data extraction from the SNDS is regulated from National Institute of Health Data (*Institut National des Données de Santé* - INDS). According to the advice of CPP, a submission to the committee in health data research (*Comité d'Expertise pour les Recherches, les Etudes et les Evaluations dans le domaine de la Santé* - CEREES) may be required. Data extraction from the SNDS needs the authorization from the French data protection commission (*Commission Nationale de l'Informatique et des Libertés* - CNIL).

This research has been registered on the site http://clinicaltrials.gov/, and on the site ENCePP http://www.encepp.eu (European Network of Centres for Pharmacoepidemiology and Pharmacovigilance).

CHANGES TO THE PROTOCOL

Any substantial change, i.e. any change that is likely to have a significant impact on the protection of persons, on the conditions of validity and on the results of the research, on the quality and safety of the products tested, on the interpretation of scientific documents that support the conduct of the research or the way in which the research is conducted, is subject to a written amendment submitted to the sponsor. The latter must obtain, prior to its implementation, a favourable opinion from the CPP.

Non-substantial changes, i.e, those that do not have a significant impact on any aspect of the research, are communicated to the CPP for information.

All changes are validated by the sponsor, and by all research stakeholders involved in the change, before submission to the CPP.

All changes to the protocol must be made known to investigators, who are participating in the research. The investigators undertake to respect the content.

[figure not shown]
Any modification that modifies participant care or the benefits, risks and constraints of the research is the subject of a new information note and a new consent form whose collection follows the same procedure above.

16. DATA HANDLING AND RECORD KEEPING

The following documents related to this research are archived by the investigator in accordance with Good Clinical Practices guidelines:

- for a period of 15 years following the end of the research
 - The protocol and any modifications to the protocol
 - Case report forms (copies) and specific auto-questionnaires
 - Source records of participants who have signed a consent form
 - All other documents and correspondence related to research
- for a period of 15 years following the end of the research
 - Original copies of the informed consent forms signed by the participants

All of the above-listed documents are the responsibility of the investigator during the regulatory archiving period. No documents may be destroyed or removed without the agreement of the sponsor. At the end of the archiving period, the sponsor will be consulted regarding the destruction of certain documents. All data, documents and reports may be subject to audit or inspection.

17. STUDY REPORTS

Within four year after the end of the research (i.e. 3-year follow-up post LPLV) or its interruption, a final report including full SNDS data analysis will be prepared and signed by the sponsor and the investigator. This report will be kept at the disposal of the competent authority.

18. RULES FOR PUBLICATION

18.1. SCIENTIFIC COMMUNICATIONS

The data analysis provided by the investigating centers is carried out by the BPE research platform of University of Bordeaux. This analysis gives rise to a written report which is submitted to the sponsor, who will forward it to the Committee for the Protection of Persons and to the competent authority.

Any written or oral communication of the results of the research must have the prior consent of the coordinating investigator and, where appropriate, of all committees that were established for the research.

The coordinating/ principal investigator undertakes to make available to the public both negative and inconclusive and positive research results.

The publication of the main results must mention the name of the sponsor, all the persons who helped in the inclusion or follow-up of participants in the research, methodologists, biostatisticians and data managers who participated in the research, health vigilance personnel who participated in the safety analysis of the participants, members of the committee(s) constituted for the research and the involvement of the laboratory NEOTRAC INC source of funding. International rules of writing and publication will be taken into account (*The Uniform Requirements for Manuscripts* of the ICMJE, April 2010).

18.2. COMMUNICATION OF RESULTS TO PARTICIPANTS

In accordance with law no. 2002-303 of 4 March 2002, the participants are informed, at their request, of the overall results of the research.

20. APPENDICES

Appendix 1 : Haute Autorité de Santé (French National Health Authority) statement on Urolift

COMMISSION NATIONALE D'EVALUATION DES DISPOSITIFS MEDICAUX ET DES TECHNOLOGIES DE SANTE

AVIS DE LA CNEDIMTS 30 mai 2017

Faisant suite à l'examen du 16/05/2017, la CNEDIMTS a adopté le projet d'avis le 30/05/2017

CONCLUSIONS

UROLIFT, implant intra-prostatique

Demandeur : NEOTRACT Inc (Etats-Unis)
Fabricant : NEOTRACT Inc (Etats-Unis)

Les modèles et références retenus sont ceux proposés par le demandeur : UL-400-4

Indications retenues :	Traitement des symptômes du bas appareil urinaire (SBAU) liés à une hypertrophie bénigne de la prostate chez les patients intolérants à un traitement médical optimal ou en cas de contre-indication aux autres traitements chirurgicaux endoscopiques.		
Service Attendu / Rendu (SA) :	Suffisant, en raison de : - son intérêt pour traiter les symptômes du bas appareil urinaire - l'intérêt de santé publique compte tenu de la dégradation de la qualité de vie engendrée par cette pathologie.		
Comparateur(s) retenu(s):	Traitement chirurgical endoscopique de résection transurétrale de la prostate		
Amélioration du SA :	ASA de niveau IV (mineure)		
Type d'inscription :	Nom de marque		
Durée d'inscription :	5 ans		

Appendix 2 : French International Prostatic Symptom Score (IPSS)

Nom:	Prénom : .				Dat	e :
IPSS : Intern	ational	Prostate	e Score	Sympto	m	
	Jamais	Environ 1 fois sur 5	Environ 1 fois sur 3	Environ 1 fois sur 2	Environ 2 fois sur 3	Presque toujours
Au cours du dernier mois, avec quelle fréquence avez vous eu la sensation que votre vessie n'était pas complètement vidée après avoir uriné?	0	1	2	3	4	5
Au cours du dernier mois, avec quelle fréquence avez vous eu besoin d'uriner moins de 2 heures après avoir fini d'uriner ?	0	1	2	3	4	5
Au cours du dernier mois, avec quelle fréquence avez vous eu une interruption du jet d'urine c'est à dire démarrage de la miction puis arrêt puis redémarrage?	0	1	2	3	4	5
Au cours du dernier mois, après avoir ressenti le besoin d'uriner, avec quelle fréquence avez vous eu des difficultés à vous retenir d'uriner ?	0	1	2	3	4	5
Au cours du dernier mois, avec quelle fréquence avez vous eu une diminution de la taille ou de la force du jet d'urine?	0	1	2	3	4	5
Au cours du dernier mois, avec quelle fréquence avez vous dû forcer ou pousser pour commencer à uriner?	0	1	2	3	4	5
	Jamais	1 fois	2 fois	3 fois	4 fois	5 fois
Au cours du dernier mois écoulé, combien de fois par nuit, en moyenne, vous êtes-vous levé pour uriner (entre le moment de votre coucher le soir et celui de votre lever définitif le matin?	0	1	2	3	4	5
 0 - 7 = léger 8 - 19 = modéré 20 - 35 = sévère 					Total =	IPSS :

Évaluation de	la qual	ité de v	ie liée a	ux symp	tômes	urinaire	es
	Très satisfait	Satisfait	Plutôt satisfait	Partagé (ni satisfait, ni ennuyé)	Plutôt ennuyé	Ennuyé	Très ennuyé
Si vous deviez vivre le restant de votre vie avec cette manière d'uriner, diriez-vous que vous en seriez :	()	1	2	3	4	5	6

Appendix 3: French Incontinence Severity Index (ISI)

Nom :	Prénom :	Date :

Incontinence Severity Index (ISI)

Merci de répondre aux questions suivantes et d'entourer le chiffre correspondant.

- 1. A quel fréquence avez vous des fuites urinaires?
 - 1 Moins d'une fois par mois
 - 2 Plusieurs fois par mois
 - 3 Plusieurs fois par semaine
 - 4 Tout les jours ou nuits
- 2. Quelle quantité d'urine perdez vous à chaque fois?
 - 1 Gouttes
 - 2 Quantité faible
 - 3 Quantité plus importante

La valeur du score correspond au produit des deux chiffres correspondants aux deux réponses.

Score ISI: ____

- 1-2 : Incontinence minime
- 3-6 : Incontinence modérée
- 8-9 : Incontinence sévère
- 12 : Incontinence très sévère

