3.2. SECONDARY OUTCOMES MEASURES

Secondary endpoints will be:

- The incremental cost/Qaly of PUL compared to transurethral surgery at 12 months
- The total hospital cost of each surgery procedure based on a top down micro-costing method performed during hospitalization stay
- Overall and specific urogenital healthcare consumptions at 4 months, 1 year and 3 years following the surgical procedure
 - Dispensed medications identified using the corresponding codes of the Anatomical Therapeutic Chemical (ATC) Classification;
 - o In- and out-patient visits;
 - Hospitalisation and their corresponding discharge diagnoses coded according to International Classification of Disease, 10th revision;
 - Medical procedures;
 - Nursing acts and physiotherapy;
 - Medical imageries and lab tests;
 - Transport;
 - Sick allowances;
 - At 4 months: all healthcare consumptions which are not reimbursed, but payed by the patient (e.g.: urinary incontinence products).

• BPH retreatment,

• Any dispensing of the following medications at 1 and 3 years after surgical procedure: alpha-blockers (ATC code G04CA) or 5-alpha-reductase inhibitors (ATC code G04CB);

 Hospitalization at 1 and 3 years after surgical procedure, with the main diagnosis of BPH (ICD-10 code N40) and the surgical procedure codes JGNE003, JGNE171, JGNJ001, JGFA005 JGFA009, JGFA015, JGFE023, JGFE365.

Urinary symptoms,

- Urinary incontinence evolution between inclusion and 4 months after surgical procedure (Incontinence Severity Index (ISI));
- International consultation on Incontinence questionnaire for Urinary incontinence short form (ICIQ-UI SF)
- Hospitalization with a discharge diagnosis ICD-10 code related to an urinary infection (code N41 for acute prostatitis or code N10 for acute pyelonephritis) at 1 and 3 years after surgical procedure;
- Hospitalization with a discharge diagnosis ICD-10 code related to urinary retention (R33) at 1 and 3 years after surgical procedure;
- Hospitalization with a discharge diagnosis ICD-10 code and/or medical procedure related to urethral stricture at 1 and 3 years after surgical procedure.

• Global quality of life,

- IPSS and IPSS-Q8 evolution between inclusion, 4 month, and 1 year after surgical procedure;
- O Jenkins sleep questionnaire between inclusion, 4 months, and 1 year after surgical procedure;
- EQ-5D-5L questionnaire (appendix 2) evolution between inclusion, 4 months, and 1 year after surgical procedure;

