11.2. STATISTICAL METHODS EMPLOYED

11.2.1. GENERALITIES

Statistical analysis will be performed using SAS® software (SAS Institute, latest current version, North Carolina, USA). Qualitative and ordinal variables will be summarized by frequencies and proportions of each modality, taking into account missingness as a modality. Continuous variables will be summarized by size, number of patients with missing data, arithmetic mean, standard deviation, median, interquartile ranges and extreme values. Confidence intervals will be estimated using Normal approximation for quantitative and qualitative relevant parameters, or bootstrapping method for costs when count < 100 patients.

Standardized mean differences (*Rosenbaum*, *Rubin*, 1985) will be estimated to measure the effect size of quantitative and qualitative baseline characteristics between groups (PUL and TURP cohorts, matched patients of PUL and SNDS cohorts).

For confidence intervals, 2-sided confidence level of 95% will be used. For all tests, a 2-sided significance level of 5% will be used:

- Proportions will be compared between two independent groups using Pearson's Chi-2 test (or Fisher's exact test when expected counts are < 5)
- Means will be compared between two independent groups using Student's t-test when normal distribution is followed (or Mann-Whitney's test when normal distribution is not followed)
- Occurrence of events (retreatment, urinary symptoms) will be estimated across time using Kaplan-Meier estimator and compared between groups with logrank test.
- Adjusted comparisons between PUL and the TURP/Laser cohorts and between PUL and SNDS cohorts will be
 performed in intention-to-treat analysis using linear regression model when it involves quantitative variables,
 and using logistic regression model adjusted on potential confounders when it involves qualitative variables.

[figure not shown]
A Statistical Analysis Plan (SAP) will be developed and will be validated before the analyses.

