Appendix 8: French traduction of Jenkins Sleep Evaluation Questionnaire

Nom:	Prénom :	Date:

Jenkins Sleep Evaluation Questionnaire

Parmi les 30 derniers jours, vous est-il arrivé :	Jamais	1 à 3 jours	4 à 7 jours	8 à 14 jours	15 à 21 jours	22 à 30 jours
D'avoir du mal à vous endormir	0	1	2	3	4	5
De vous réveiller quelques fois dans la nuit sans avoir de problème à vous rendormir	0	1	2	3	4	5
De vous réveiller une ou plusieurs fois dans la nuit (y compris vous réveiller trop tôt), et avoir du mal à vous rendormir	0	1	2	3	4	5
De vous réveiller après votre durée de sommeil habituelle en étant fatigué ou épuisé	0	1	2	3	4	5

CIQ-UI SF)	rision of international Consultation on I	ncontinence Questionnaire-Urinary Incontin	nence Sh
Numéro	ICIQ-UI Short Form (Fr	J J M M M A A Date	
personnes ont		n temps. Nous essayons de savoir combien les ne. Veuillez répondre aux questions suivantes, RE DERNIERES SEMAINES.	
1 Votre date	e de naissance:	JOUR MOIS ANNÉE	
2 Sexe (coc	hez la réponse):	Femme Homme	
3 A quelle fr	équence avez-vous des pertes d'urine?	(ne cochez qu'une seule réponse) jamais environ une fois par semaine deux à trois fois par semaine environ une fois par jour plusieurs fois par jour tout le temps 0 1 2 4 tout le temps 5	
	la quantité habituelle de vos pertes d'urir	pertes d'urine, selon votre estimation . ne (avec ou sans protection)?	
	la quantité habituelle de vos pertes d'urin z qu'une seule réponse)		
(Ne coche	e générale, à quel point vos pertes d'urine? Entourez un chiffre entre 0 (pas du tout) et 0 1 2 3 4 5 6 7 tout	nulle 0 une petite quantité 2 a moderate amount 4 a large amount 6 e vous dérangent-elles dans votre vie de	
5 De manière tous les jours	e générale, à quel point vos pertes d'urine? Entourez un chiffre entre 0 (pas du tout) et 0 1 2 3 4 5 6 7 tout	nulle une petite quantité a moderate amount a large amount 6 e vous dérangent-elles dans votre vie de 10 (vraiment beaucoup) 8 9 10 Vraiment beaucoup : ajoutez les scores 3+4+5	

Merci d'avoir pris le temps de répondre à ces questions.

Copyright © "ICIQ Group"

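### The ISI form offers no 'never' answer and cannot score 0, which distorts the ISI change endpoint for men without leakage

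*Protocol*

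**What the plan says.** Protocol section 3.2 lists, under urinary symptoms, "Urinary incontinence evolution between inclusion and 4 months after surgical procedure (Incontinence Severity Index (ISI". The ICIQ-UI SF is the next item in the list, with no time point or change attached. Sections 9.3.2, 9.6 and 9.7 have both questionnaires completed at inclusion, month 4 and month 12, and section 11.2.4 describes the values of both scores over the first year.

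Appendix 3 prints the ISI form. Item 1 (frequency) starts at "1 Moins d'une fois par mois" and ends at "4 Tout les jours ou nuits". Item 2 (quantity) starts at drops, scored 1, and ends at "3 Quantité plus importante". The scoring rule is "La valeur du score correspond au produit des deux chiffres correspondants aux deux réponses". The printed grades are 1-2 minimal, 3-6 moderate, 8-9 severe and 12 very severe. There is no grade for 0 and no instruction for a man who does not leak.

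The ICIQ-UI SF form, printed after Appendix 8, does have a zero. Its frequency options begin "jamais environ une fois par semaine", and its quantity item begins at *nulle*, scored 0.

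Section 11.2.1 says qualitative and ordinal variables are summarised "taking into account missingness as a modality".

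**The concern.** Eligibility (sections 5.1.1 and 5.1.2) rests on symptomatic BPH, IPSS, flow rate and prostate volume. Leakage is not required, so continent men can be enrolled, and such a man has no correct answer on the ISI. Either he circles 1 and 1 and is graded incontinent, or he leaves the form blank.

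The endpoint is a change score, and sections 1.4 and 1.5 treat persistent incontinence as a harm of standard surgery that PUL should not worsen and may reduce. The transitions from dry to leaking and from leaking to dry are therefore of direct interest, and the printed form has no value for the dry end of either one.

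Blanks would also depend on continence itself and so would not be random. If ISI grades are tabulated with missing as a category, dry men would be counted together with men who simply did not answer.

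**Working it through.** **Inputs.** From Appendix 3: item 1 in {1, 2, 3, 4}, item 2 in {1, 2, 3}, score = item 1 × item 2.

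**Step 1: reproduce the printed scale.** All 12 answer pairs:

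| Frequency | Quantity 1 | Quantity 2 | Quantity 3 |
|---|---|---|---|
| 1 | 1 | 2 | 3 |
| 2 | 2 | 4 | 6 |
| 3 | 3 | 6 | 9 |
| 4 | 4 | 8 | 12 |

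The attainable scores are 1, 2, 3, 4, 6, 8, 9 and 12. The four printed grades cover exactly these values, so options and grades agree with each other. The minimum is 1 × 1 = 1, and 0 cannot occur.

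**Step 2: man dry at inclusion who circles 1 × 1, then leaks at month 4 with score s.** The true change is s − 0 = s. The recorded change is s − 1, one point too small for every s. By answer pair:

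- 1 pair (1 × 1): recorded change 1 − 1 = 0, so the new leakage is invisible.
- 2 pairs (1 × 2 and 2 × 1): recorded change 2 − 1 = +1, but the grade stays *Incontinence minime*.
- 9 pairs (s of 3 or more): the grade rises, with the change understated by one point (for example 12 − 1 = 11 instead of 12).

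The check is 1 + 2 + 9 = 12. These are counts of possible answers, not probabilities.

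**Step 3: man dry at inclusion who leaves the form blank.** There is no baseline score, so no ISI change can be calculated, whatever he reports at month 4.

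**Step 4: man leaking at inclusion with score s, dry at month 4.** The true change is 0 − s = −s. If he circles 1 × 1, the recorded change is 1 − s, so the improvement is understated by one point and he is still graded incontinent. For s = 1 the recorded change is 0. If he leaves the form blank, the change is missing.

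**Step 5: with a zero added.** The attainable scores become 0, 1, 2, 3, 4, 6, 8, 9 and 12. A dry man scores 0, any new leakage gives a positive change and leaves the zero category, and resolution is recorded as 0.

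**Step 6: what the ICIQ-UI SF retains.** Its minimum is 0 and it is completed at the same three visits, so a change from no leakage to leakage can be measured there. It covers the last four weeks, and its first frequency above *jamais* is about once a week. A man who leaks less than once a month, which is a valid ISI frequency of 1, may therefore truthfully answer *jamais*. The two forms do not define zero identically, and that limits how far one can repair the other.

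**The case against.** A reader might infer that new incontinence after surgery is lost to this trial. The documents do not support that. The ICIQ-UI SF is a listed outcome, has a zero and is completed at every visit where the ISI is. Section 9.2 also schedules complications and adverse effects through month 12, and section 3.2 collects unreimbursed products, naming those for incontinence, at 4 months. Even on the ISI alone, 9 of the 12 possible later answers move a man scored 1 at baseline to a higher grade.

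A reader might also infer that most men would have no usable ISI change. The protocol gives neither the proportion continent at inclusion nor how such men would answer, so no figure can be put on this.

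It can fairly be said that coding of blanks belongs in the data management plan, the data validation plan or the SAP, none of which is shown. That stands: the absence of a coding rule from the protocol is not the finding. The finding is a form and scoring rule, fixed in the protocol, that give a dry man a wrong value. A later plan can repair this afterwards but cannot supply an answer that the patient was never offered.

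Two further cautions stand. The protocol version is dated 31/01/2023 and the summary plans inclusion for Q2 2021 to Q2 2023, so many baseline forms may already be complete. And the printed form cites a published source that cannot be inspected here, so the change departs from the instrument as cited.

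**Conclusion.** The point holds for the ISI change endpoint. As printed, the form cannot record continence, so a man without leakage at inclusion or month 4 is graded minimally incontinent or is missing. The size per man is fixed by arithmetic: one point of understatement wherever a dry state is forced to 1, concealment within the lowest grade when the leakage itself scores 1 or 2, and no change score at all when either form is blank. The number of men affected is unknown.

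This is one secondary endpoint, backed by a second incontinence questionnaire, and the primary endpoint is untouched. It is worth correcting because the repair is cheap and this is the only incontinence measure that section 3.2 defines explicitly as a change.

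The conclusion assumes that text extraction did not drop a zero line from Appendix 3. The grades starting at 1-2 and matching the printed options make such a loss unlikely.

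**What to change.** - **Forms still to be completed:** add *Jamais (0)* to item 1, with item 2 skipped and score 0 labelled as no incontinence.
- **Forms already completed:** set ISI to 0 only when the ISI is blank and the same-visit ICIQ-UI SF shows frequency *jamais* and quantity *nulle*. Keep answered ISI forms as given. Setting 0 whenever the ICIQ-UI SF frequency is *jamais* would overwrite valid answers from men who leak less than once a month.
- **Sensitivity analysis only:** recode 1 × 1 answers to 0 where the same-visit ICIQ-UI SF frequency is *jamais*.
- **Reporting:** give the transitions from 0 to above 0 and from above 0 to 0 at months 4 and 12, with the ICIQ-UI SF change alongside.

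The cost is one added answer and one derivation rule, with no new visit or instrument. The downsides are small but should be stated. Two form versions will coexist: a man dry throughout who circled 1 × 1 on the old form and *Jamais* on the new one shows 0 − 1 = −1, a spurious improvement that the sensitivity analysis would expose. The four-week recall of the ICIQ-UI SF may also miss leakage that occurs less than once a month, so some derived zeros will be wrong.
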